12.0 Data Management

All data will be stored in the Redcap database as well as in paper documentation. Information about the participants (including their identifiable private information) may have all their identifiers removed and used for future research studies or distributed to other researchers for future research without additional informed consent. After participation, RedCAP data will be downloaded in Excel format to the secure MUSC server. Paper documentation will be stored in locked cabinet within a locked office of the study team. In terms of publication, data will be published in aggregate form, so individual participants will not be identifiable in the final manuscript. No identifying information will be published.

Confidentiality and Quality Control: All study personnel will complete Social-Behavioral-Educational research CITI training, and also complete in-lab training regarding data security practices. Study personnel will be trained in the IRB protocol. The investigator, and co-investigators will be available to monitor data collection to ensure quality, confidentiality, and adherence to the IRB protocol.

All study's procedures will take place at the MUSC [name] Neuroimaging Center. Regarding documentation, participant names will appear only on the IRB-approved Consent and HIPAA.

The RESTORE registry (Pro#00037803), from which this study will recruit subjects, also serves as a data analysis tool by which interdisciplinary teams may share data across projects and provide MUSC's stroke recovery research community with a more complete registry with key stroke elements. Some subjects may have participated or will participate in other stroke related research studies at MUSC. Sharing data from this and other stroke research studies with RESTORE will allow for more targeted recruitment efforts in the future and could reduce the burden placed on subjects by reducing the duplicative efforts of collecting common data and physical function assessments requested by multiple studies and storing them in one centralized and secure location. The third Aim of this study leverages this ability, as other studies will be better able to target their recruitment based on the information collected in these assessments. De-identified information/data will only be shared once study is completed.

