1.0 Objectives / Specific Aims

In this study, our main goal is to establish transcutaneous auricular vagus nerve stimulation (taVNS) as an effective non-invasive neuromodulation method for analgesia of post-stroke upper extremity pain.

We will recruit up to 20 participants with chronic post-stroke upper extremity pain from the greater Charleston area using MUSC COBRE resources. Participants are required to have an ischemic or hemorrhagic stroke that occurred at least 6 months prior and are currently suffering upper extremity pain. Each participant will undergo an in-person visit to our lab at MUSC [name]. They will first finish the pain questionnaires and have quantitative sensory testing (QST) conducted to determine baseline pain thresholds. Participants will then receive 30 minutes of taVNS (either active or sham). Upon the completion of the stimulation intervention, they will then be tested for another QST and pain questionnaires. All research is being done at MUSC [name] Center for Biomedical Imaging.

Aim 1: Test the safety and feasibility of taVNS in participants with chronic post-stroke upper extremity pain.

Over the last 8 years, our group has demonstrated that taVNS is safe and feasible in several different populations in our previous studies. Specifically, we have demonstrated that taVNS is well tolerated and safe for participants with chronic stroke in our previous clinical trial ([name] et al., 2023, [name] et al., 2023). In this study, we will further verify the safety and feasibility of taVNS in the population with chronic post-stroke upper extremity pain.

Aim 2: Investigate whether taVNS can modulate pain in this population compared to sham.

In this single-visit, single-blinded, sham-controlled pilot trial, we will compare changes in post-stroke upper extremity pain scores and pain threshold derived from QST before and after a 30-minute taVNS intervention, as well as between active and sham taVNS. The findings will help us understand whether taVNS can modulate pain in this population.

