3.0 Intervention to be studied (if applicable)

The intervention we are studying is transcutaneous auricular vagus nerve stimulation (taVNS) which is simply electrical nerve stimulation administered at the ear which targets the auricular branch of the vagus nerve. In this study, taVNS will be administered using the Spark Sparrow Ascent System which is a non-significant risk

investigational device. The Spark Sparrow Ascent System is based on an FDA-cleared device provided by Spark Biomedical and has completed all safety and compliance testing. taVNS is a non-significant risk method that has been approved by the MUSC IRB for many ongoing taVNS trials. [name] are the PI or Co-I of more than seven ongoing taVNS trials. The Spark device summary has been uploaded to the MUSC IRB portal.

In this study, we will use the device as an anti-pain device in participants with chronic post-stroke upper extremity pain. Participants will be randomized to receive 30-minute active taVNS (tragus and cymba conchae) or sham taVNS (earlobe) during their in-person visit. In prior studies in our laboratory, we demonstrated that taVNS can be safely and feasibly administered in chronic stroke populations ([name] et al., 2023, [name] et al., 2023).

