5.0 Inclusion and Exclusion Criteria/ Study Population

Twenty participants with upper extremity post-stroke pain of all ethnic and racial categories will be accepted into this study protocol. No preference will be given based on race, gender, or ethnicity. Pregnant females and children under the age of 18 will be excluded for safety reasons.

Inclusion Criteria:

- Age 18-80
- Have the capacity and ability to provide one’s own consent in English and sign the informed consent document.
- Ischemic or hemorrhagic stroke that occurred at least 6 months prior
- Unilateral stroke lesions in the left hemisphere
- Right upper extremity pain

Exclusion Criteria:

- Primary intracerebral hematoma or subarachnoid hemorrhage
- Documented history of dementia

- Documented history of uncontrolled depression or psychiatric disorder
- Uncontrolled hypertension despite treatment, specifically SBP (Systolic Blood Pressure) / DBP (Diastolic Blood Pressure) $\geq 180/100$ mmHg
- Pregnancy

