8.0 Recruitment Methods

This study will recruit from the Registry for Stroke Recovery (RESTORE-Pro#00037803, IRB approved 9/6/14) which is a research tool sponsored by the National Institutes of Health (NIH) Center of Biomedical Research Excellence (COBRE) in Stroke Recovery with subjects consented for future contact to support stroke recovery research conducted at MUSC. RESTORE staff will query the registry for potential subjects and provide the Principal Investigator (PI) with the contact information of subjects who meet their criteria. The PI or research staff will then contact subjects to confirm whether they are interested in the study following the cold call recruitment script. Additionally, RESTORE staff can also give rack cards to interested RESTORE (stroke registry) individuals. They will be further screened for potential enrollment.

[figure not shown]

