18.0 Drugs or Devices

tAN Device (Spark Biomedical Sparrow Ascent)

tAN has been determined a non-significant risk determination of this device. We are using the Spark Sparrow Ascent tAN system outlined in this document, based on the FDA-cleared Sparrow System (K201873). IRB 1 has consistently given NSR status for all prior tAVNS studies at MUSC, including studies in stroke patients ([name]), brain damaged newborns learning to feed ([name], [name]), Parkinson's Disease ([name], [name]) and healthy volunteers ([name], [name]).

QST Pain Device (Medoc Pathway TSA2)

Medoc's TSA2 offers thermal stimulation in the full range from sensation to pain, in heat and cold, using one or two thermodes simultaneously. A wide variety of thermodes is available for each body site or stimulation profile. Excellent temperature control and fast rates make the device accurate, the test repeatable, and suitable for a great number of applications. Medoc has been developing and manufacturing QST devices in the thermal, pressure, and vibratory modalities for over 30 years. This system has been IRB-approved here at MUSC in prior work conducted by the Co-Is ([name], [name]).

References

BADRAN, B. W., PENG, X., BAKER-VOGEL, B., HUTCHISON, S., FINETTO, P., RISHE, K., FORTUNE, A., KITCHENS, E., O'LEARY, G. H. & SHORT, A. 2023. Motor Activated Auricular Vagus Nerve Stimulation as a Potential Neuromodulation Approach for Post-Stroke Motor Rehabilitation: A Pilot Study. *Neurorehabilitation and Neural Repair*, 15459683231173357.

BAO, S.-C., KHAN, A., SONG, R. & TONG, R. K.-Y. 2020. Rewiring the lesioned brain: electrical stimulation for post-stroke motor restoration. *Journal of stroke*, 22, 47.

BITTAR, R. G., KAR-PURKAYASTHA, I., OWEN, S. L., BEAR, R. E., GREEN, A., WANG, S. & AZIZ, T. Z. 2005. Deep brain stimulation for pain relief: a meta-analysis. *Journal of clinical neuroscience*, 12, 515-519.

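### Some recruits may have had taVNS before; nothing excludes or records this, and the earlobe sham differs from active by a site the participant can feel, so blinding in Aim 2 is at risk

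*Protocol*

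**What the plan says.** **Recruitment.** Protocol Section 8.0: "This study will recruit from the Registry for Stroke Recovery". It describes the registry's members as "subjects consented for future contact to support stroke recovery research conducted at MUSC". Registry staff query it for people who meet the study's criteria, and the team then contacts them. No other source is named.

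**Other studies.** Section 12.0, in a paragraph on data sharing: "Some subjects may have participated or will participate in other stroke related research studies at MUSC".

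**The group's earlier taVNS work.** Section 1.0, Aim 1: "we have demonstrated that taVNS is well tolerated and safe for participants with chronic stroke in our previous clinical trial". Section 18.0 refers to a non-significant-risk status given "for all prior tAVNS studies at MUSC, including studies in stroke patients". Section 3.0 adds that members of the team "are the PI or Co-I of more than seven ongoing taVNS trials", without naming the populations.

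**Arms.** Section 3.0: "Participants will be randomized to receive 30-minute active taVNS (tragus and cymba conchae) or sham taVNS (earlobe) during their in-person visit". Section 10.0 gives the sham the cymba concha parameters and sets intensity at twice the perceptual threshold for everyone.

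**Blinding and outcomes.** Aim 2 in Section 1.0 calls the trial single-blinded and sham-controlled. The efficacy outcomes in Section 4.0 are a 0-10 pain rating and button-press heat thresholds.

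**Eligibility.** Section 5.0 lists five exclusions: primary intracerebral hematoma or subarachnoid hemorrhage, dementia, uncontrolled depression or psychiatric disorder, uncontrolled hypertension, and pregnancy. Neither these nor the five inclusion criteria mention earlier taVNS.

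**The concern.** A sham that differs from active by location works as long as participants do not know which location is the real one. A person new to taVNS has no reference point. A person who has worn an active montage may have one. Because stimulation in both arms is set above the perceptual threshold, the site is felt throughout the session.

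Both kinds of efficacy measure depend on the participant's own judgement: the rating directly, the thresholds through the moment at which the button is pressed. If a participant in the sham arm recognises the earlobe as sham, or one in the active arm recognises the familiar site, expectation can enter the post-session values. Aim 2 rests on the contrast between arms, and with 20 participants in total a few such people carry noticeable weight.

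**Working it through.** The plan gives no figure on this point, so there is none to reproduce. The check is a reading of the sections against each other, followed by one conditional illustration.

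**Step 1. Can a taVNS-experienced person be in the pool?** Section 8.0 names a registry serving stroke recovery research at the institution generally. Section 12.0 foresees subjects who have been in other stroke studies there. Sections 1.0 and 18.0 place earlier taVNS studies in stroke patients at the same institution, and the reference list includes a post-stroke motor pilot and an imaging study of taVNS in chronic stroke. Together these make overlap possible. None of them states it.

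**Step 2. Would such a person be stopped?** Section 5.0 has no relevant criterion. The registry query in Section 8.0 follows the study's criteria, so it would return that person as eligible. The phone screen in Section 10.0 has no stated question on it.

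**Step 3. Would the exposure be known at analysis?** The baseline battery in Section 10.0 covers demographics, pain screening, substance use, pain interference, physical function, sleep, depression and anxiety. Stimulation history is not among the listed domains. No washout or stratification on it appears, and no check of blinding is described.

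**Step 4. Could the arm be recognised?** Tragus and cymba conchae against earlobe (Sections 3.0 and 10.0) is a difference in felt position. Recognition needs three further things: that the person earlier received active stimulation, at a comparable site, and knows or suspects that it was active. The documents are silent on all three.

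**Step 5. How likely is at least one experienced participant?** Let p be the share of the pool with earlier taVNS. The documents give no value; p is assumed here and could be zero. The chance of at least one among n participants is 1 − (1 − p)^n. The allocation ratio is not stated, so a sham arm of 10 assumes 1:1.

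| Assumed p | At least one of 20 | At least one of 10 in sham |
|---|---|---|
| 5% | 1 − 0.95^20 = 64% | 1 − 0.95^10 = 40% |
| 10% | 1 − 0.90^20 = 88% | 1 − 0.90^10 = 65% |
| 20% | 1 − 0.80^20 = 99% | 1 − 0.80^10 = 89% |

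The table concerns exposure, not recognition. It shows only that a small share would be enough to bring experienced people into a trial of this size. One such person would be 1/10 = 10% of an arm. It does not measure bias.

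**The case against.** The strongest case against is that every link after the missing criterion is inferred.

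- **Shared recruitment.** A reader might infer that the group's taVNS trials drew on this same registry. No section says so. Section 12.0 speaks of stroke studies in general, and the requirement of a left-hemisphere lesion and right arm pain narrows any overlap by an unknown amount. This stands: overlap is a possibility.
- **Ongoing trials.** The trials counted in Section 3.0 have no stated populations, and Section 18.0 lists newborns, Parkinson's disease and healthy volunteers as well as stroke. They are weak support for overlap.
- **Concurrent participation.** A reader might infer that members are in other studies at the time of the visit. Section 12.0 speaks of past and future participation; that concurrent participation is possible follows only from the silence of Section 5.0.
- **Recognition and direction.** A reader might infer that blinding fails in experienced people and that the result must favour active. Neither is shown. Someone who had taVNS before without relief could expect nothing from it.
- **Carry-over.** Allocation is randomised and baseline is taken at the same visit, so any residual effect would mainly add noise or chance imbalance.
- **Impact.** The primary outcome is safety and feasibility in a single-visit pilot. Prior acceptance of the device might colour feasibility, but that needs the same unproven overlap.

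These points limit the wording and the size. They do not remove the gap. Eligibility belongs in the protocol, and an analysis plan cannot reliably recover an exposure that was never asked about. Pilot status does not help either, since Aim 2 expressly compares with sham.

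**Conclusion.** The concern holds as a risk. The plan as written admits people who may have had taVNS, does not record it, and uses a sham distinguishable by felt site in a single-blinded trial with participant-reported efficacy outcomes. The comparison at risk is the secondary one in Aim 2, probably but not certainly in favour of active. Safety and feasibility are less exposed.

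No size can be given. The share of experienced recruits, the rate of recognition and its effect on ratings are all absent from the documents, and a bias in pain-scale points would only multiply assumed inputs. The conclusion rests on two assumptions: that the registry and the earlier taVNS studies in stroke overlap to some degree, and that some exposed people could tell the active site from the earlobe. Both are plausible and neither is documented. The change is worth making because it is cheap and cannot be made afterwards.

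**What to change.** Add to the exclusion criteria in Section 5.0: previous or current taVNS/tAN. Ask about it at the phone screen already described in Section 10.0, and check the answer against registry participation data where these are available.

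If the pool then proves too small, drop the exclusion but record prior exposure before randomisation, and report the active-sham comparison in taVNS-naive participants as well as in all participants. A blanket exclusion of anyone in another interventional study would go wider than this problem and is not needed for it.

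The cost is one eligibility line, one screening question and a somewhat smaller pool from which to find 20 participants.

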13.0 Provisions to Monitor the Data to Ensure the Safety of Subjects

There are three areas in which safeguards to protect subjects from undue risk require discussion. These include: 1) procedures used to obtain informed consent, 2) procedures used to ensure confidentiality of the subject data, and 3) procedures used to minimize possible risks associated with the laboratory procedures. Regarding informed consent, participants are fully advised on the research procedures to be used, the amount of time required of them, the possible risks and benefits of the procedures, their right to refuse participation in the study without prejudice, their right to terminate participation at any moment without prejudice, and the name and telephone number of the principal investigator. All subjects will be required to have the capacity to consent. Regarding confidentiality, subjects are informed that the information they provide will be kept strictly confidential, with access limited to the research staff. Participation in the study will be treated as confidential, as will all records. The identity of subjects will be protected with alphanumeric codes. All data will be kept in locked file cabinets or on secure servers designed for use and access by the study team only.

We do not anticipate any adverse events to occur in this study, however, the experienced research team has a long-standing record of recording and reporting unanticipated adverse events to the IRB. We will report any adverse event within 48 hours to the IRB.

14.0 Withdrawal of Subjects

Participants will be informed during consenting that they are free to withdraw from the study at any time. They will be informed that they are not obligated to participate once the study is initiated and in particular will be reminded prior to taVNS/VNS stimulation they may discontinue stimulation and/or the experiment at any point. taVNS has been a very safe procedure and we do not anticipate subject withdrawal due to taVNS side effects. No participants in previous studies utilizing taVNS have been forced to withdraw for medical or physiological purposes, and we do not anticipate any issues during this study. If participants begin to experience ear pain, an attempt can be made on the other ear, as well as a reduction in the intensity of stimulation before termination would be required. We will be monitoring the stimulation session and if a patient is extremely sensitive to the device we might consider terminating. In that case, the participant and their guardian would be informed of the need for termination.

15.0 Risks to Subjects

Ear Stimulation:

Ear stimulation is safe, however, there are some risks associated with stimulating the ear: There may be local discomfort. This will likely be temporary. In extreme cases, burns might occur. We will monitor any potential burns via direct communication with participants and will stop stimulation and advise subjects to apply vitamin E cream. The tissue surrounding the ear may be sensitive, sore, or feel slight numbness. Hopefully, this will be temporary and will go away after the stimulation is turned off.

Safety in Case of Pregnancy:

This protocol will exclude pregnant women. The risks of using taVNS with pregnant women are currently unknown. If in the screening and consent a patient is a woman of childbearing age, they will be tested prior to receiving any taVNS.

Potential Headache, Dizziness, and Facial Pain:

Ear stimulation might cause headaches or face pain, which should resolve shortly after treatment.

Potential Decrease in Heart Rate:

Ear stimulation may slow heart rate. In rare cases (less than 1%) decreased blood pressure or fainting may occur. We expect no significant changes in heart rate or blood pressure, or fainting to occur. For the initial sessions, all subjects will be stimulated while they are seated, never standing. We expect no significant changes in heart rate or blood pressure, but if this occurs, the study team will evaluate the situation and either decide that the patient should be dropped from the study, or do all sessions lying on a couch, or with lower doses.

QST Pain Assessments:

The Medoc pain assessment system has been used safely by Co-I [name] and others for over a decade now. The pain is unpleasant but there are limits to the amount of pain, and there have been no adverse events over 5 prior MUSC IRB-approved pain studies using this approach. Some participants may report feeling anxious before experiencing a painful stimulus, however, this is rare and if occurs, the participant will be able to request to stop voluntarily.

Unknown Risks:

There is always the possibility of other risks for a relatively new technology. The Study team will let the participant know if they learn anything that might make the participant change their mind about participating in the study.

Loss of Confidentiality:

There is a risk of a loss of confidentiality of personal information. Subjects are informed that the information they provide, as well as participation in the study, will be kept strictly confidential, with access limited to the research staff. The identity of subjects in databases will be protected with alphanumeric codes. All data will be kept in locked file cabinets or on secure servers designed for use and access by Study Team members only.

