4.0 Study Endpoints (if applicable)

Primary Outcome: *Safety and Feasibility*

The main outcomes of this pilot trial will be the safety and feasibility of implementing taVNS in the population with chronic post-stroke upper extremity pain.

Secondary Outcomes: *Quantitative Sensory Testing (QST)*

We will systematically determine information about A β (sensory), A δ (pain), and C (pain tolerance) fiber activity with a 30 \times 30 mm thermode attached to the non-affected forearm (left arm) of participants (TSA2 thermode; Medoc, Durham, NC, USA). Using the TSA2, we will determine heat sensory, pain, and tolerance thresholds using the method of limits, beginning at 32°C and increasing by 0.5°C per second. Participants will be asked to press a button (to record temperatures) when the stimulus is first detected (sensory threshold), when it becomes painful (pain threshold), and then when the stimulus is intolerable (pain tolerance). When ‘intolerable’ is indicated, the thermode ceases heating and quickly returns to 32°C. This is repeated for 5 trials to obtain average sensory, pain, and tolerance thresholds. We will acquire QST data before and after the 30-minute taVNS. We will explore the analgesic effects by comparing the pre- and post-intervention QST ratings.

Secondary Outcomes: *Subjective Pain Ratings*

Participants will rate their post-stroke upper extremity pain intensity before and after the taVNS using a standard numeric pain rating scale (0-10). We anticipate participants will rate lower pain intensity post-intervention.

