10.0 Study Design / Methods

Study Overview:

After determining eligibility and interest, written informed consent will be obtained from participants at the MUSC Center for Biomedical Imaging. After consent is obtained, the participants will then complete a pregnancy test and conduct a brief daily life functioning battery. Enrolled participants will start the experiment. They will first finish the subjective pain rating and have quantitative sensory testing (QST) conducted to determine baseline pain thresholds. Participants will then receive 30 minutes of tVNS (either active or sham). Upon the completion of the stimulation intervention, they will then be tested for another subjective pain rating and QST. The timeline of the experiment and group assignment overview are displayed below.

Experiment Overview – Investigate the anti-pain effect of taVNS in chronic post-stroke upper extremity pain

Recruitment, Screening, and Consent Procedures:

Recruitment will be conducted by the study team utilizing the MUSC RESTORE list to identify and contact prospective chronic stroke patients. Participants who are found to be appropriate candidates will be offered to be phone screened and educated regarding the study's details. If interested in participating in the study, they will be consented and enrolled into the study's protocol. Additionally, RESTORE staff can also give rack cards to interested RESTORE (stroke registry) individuals. If interested in participating in the study, they will be consented and enrolled into the study's protocol.

Daily Life Function Battery:

All participants will complete a daily life function battery after being enrolled. This battery includes the following questionnaires in specific life domains that will be used to identify baseline characteristics of individuals: Demographics; Pain Screening; Substance Use: TAPS; Pain Intensity & Interference: PEG; Physical Functioning/QDL: PROMIS Physical Functioning 6b; Sleep: PROMIS Sleep Disturbance 6a; Sleep: Sleep Duration; Depression: PHQ9; Anxiety: GAD7.

Pregnancy Test Procedures:

If participants are a person of childbearing age, they will be provided with a pregnancy test strip. After completing the pregnancy test, participants with negative results will be asked to continue to the remaining study procedures, whereas those with a positive result will be debriefed and released.

Subjective Pain Rating:

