channels of stimulation (auricular vagus, auricular trigeminal, and both). Two individual stimulation frequencies will be set: 15 Hz at cymba concha and 100 Hz adjacently anterior to tragus. The pulse duration will be set to 250 μ s for all participants. The stimulation intensities delivered (in mA) will be a standardized 2X Perceptual Threshold. This means that all individuals will first have a perceptual threshold conducted, during which incremental increases and decreases in current intensity will be applied until the participant barely feels the stimulation. That is considered the perceptual threshold. All stimulation then will be delivered at 2X this value. Perceptual threshold will be conducted at the beginning of the taVNS intervention. This is how we have conducted stimulation at MUSC in prior IRB-approved studies which have been safe and rated comfortable and not painful. Sham stimulation will be administered at identical parameters of cymba concha, however, the electrodes will be attached to the earlobe, which is not believed to have a high density of cranial nerve innervation. If the participant states that the stimulation intensity is discomforting or imperceivable in any of the stimulation groups, the researcher will gradually decrease until a comfortable stimulation intensity is achieved. The taVNS session will last for 30 minutes.

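### Burns are checked only by talking with participants: section 15.0 and the taVNS procedures could cheaply add a skin look and a record at the electrode sites

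*Protocol*

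**What the plan says.** Protocol section 15.0 (Risks to Subjects, Ear Stimulation) names the hazard: "In extreme cases, burns might occur". It then gives the method of detection: "We will monitor any potential burns via direct communication with participants". The response is to stop stimulation and advise a vitamin E cream. The next sentence of that paragraph lists soreness, sensitivity and mild numbness of the tissue around the ear as possible effects.

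Other sections bear on the same point:

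- Section 4.0 makes safety a main outcome: "The main outcomes of this pilot trial will be the safety and feasibility of implementing taVNS".
- Section 1.0, Aim 2, describes the design: "In this single-visit, single-blinded, sham-controlled pilot trial".
- Section 10.0, taVNS Procedures, covers the perceptual threshold, stimulation at twice that value, and what happens on a complaint: "the researcher will gradually decrease until a comfortable stimulation intensity is achieved".
- Section 10.0, Study Overview, lists what follows stimulation: "Upon the completion of the stimulation intervention, they will then be tested for another subjective pain rating and QST".
- Section 14.0 allows a change of side: "If participants begin to experience ear pain, an attempt can be made on the other ear". It also says: "We will be monitoring the stimulation session and if a patient is extremely sensitive to the device we might consider terminating".
- Section 13.0 commits the team to reporting any adverse event to the IRB within 48 hours.

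**The concern.** The protocol is not silent on how burns are found. It fixes a method, and that method depends on the participant feeling something and saying so. One of the side effects listed beside it, numbness, acts directly on the ability to feel something.

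This matters because safety is one of the two things the trial is mainly meant to show. A burn is the one skin injury that the protocol names, yet no planned observation of the skin is asked for. With a single visit and no follow-up contact described, a mark that is neither mentioned nor noticed that day has no later scheduled chance of being recorded. A statement that no burns occurred would then mean only that none was reported and none was noticed by chance.

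**Working it through.** The protocol gives no burn rate, safety threshold or safety-based sample size, so there is no figure to reproduce. The check is to go through each place where a skin look or skin record could stand.

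1. **Before stimulation** (section 10.0): questionnaires, pregnancy test, pain rating, quantitative sensory testing, perceptual threshold. No look at the ear.
2. **During stimulation** (sections 10.0, 14.0, 15.0): verbal communication, lower current on complaint, a possible change of ear, and session monitoring. The monitoring sentence is tied to a participant being unusually sensitive to the device and does not say what is looked at. The change of ear comes with no request to look at the first ear.
3. **After stimulation** (sections 1.0 and 10.0): pain rating or questionnaires, and sensory testing. The thermode goes on the left arm, so this testing does not examine the ear.
4. **Later**: no second visit or follow-up contact is described.
5. **Adverse events** (section 13.0): a time limit for reporting events once found, with no statement of how they are sought.

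Skin records requested in the text at hand: 0 in up to 20 participants × 1 session = 20 sessions.

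Size of the remedy, with 20 participants (section 6.0), one session each, and two scheduled looks (attachment and removal):

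- 20 × 1 × 2 = 40 looks.
- The time per look is an assumption, 20 to 30 seconds, because the protocol gives no figure.
- Lower end: 40 × 20 s = 800 s, about 13 minutes. Upper end: 40 × 30 s = 1,200 s = 20 minutes.
- Per participant: 2 × 20 s = 40 s to 2 × 30 s = 60 s.

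Looks prompted by discomfort, numbness or a change of ear come on top and cannot be counted in advance. These figures measure the cost of the change. They say nothing about how many burns would be missed.

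**The case against.** The strongest reply is that this is an operational detail, not an error. The sentence in section 15.0 is about protecting participants. It says nothing false, and it does not claim that talking is the only way safety events will be recorded. A line on a session form is often set in working procedures that are not part of the protocol.

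The safeguards also cover most realistic cases. Current is set individually and lowered on complaint, staff monitor the session, participants are reminded that they may stop, and staff remain for the testing afterwards. Any adverse event goes to the IRB, whether or not the participant raised it. What is left is a mark that is unfelt, unmentioned and also unnoticed by staff.

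Much of this stands, and it is why the point is small. It does not remove the point. The protocol states a detection method that can be improved at almost no cost. None of the safeguards is a skin look or produces a skin record, and a clinical inspection is not something usually left to a statistical analysis plan.

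Three stronger readings are tempting and are not supported:

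- *Burns will be missed.* The documents give no burn rate and no detection rate, describe burns as extreme cases, and report earlier use as safe.
- *These participants cannot feel the ear.* Numbness is listed only as a possible effect that is hoped to pass. No prior loss of ear sensation is described, and setting the perceptual threshold requires the participant to feel the current at the start.
- *The protocol has no skin check anywhere.* The numbering runs from section 10.0 to 12.0, the timeline figure is not shown, and the consent pages were removed. The absence is confirmed only for the text at hand.

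**Conclusion.** The point holds as a cheap improvement of low severity. In the text at hand, the named burn check rests on what participants say, a listed side effect could weaken it, and no skin inspection or record is requested in any of up to 20 single-visit sessions, although safety is a main outcome.

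The expected effect on the trial's conclusions is small, and nothing shows that any conclusion would change. The verdict assumes that section 11.0 and the other parts not shown contain no skin check. It also accepts that staff would probably see an obvious mark at electrode removal. What is lacking is a uniform record, kept in the same way in two groups whose electrodes sit at different sites: tragus and cymba conchae for active, earlobe for sham.

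**What to change.** Keep the verbal communication and add to section 15.0 and to the taVNS procedures in section 10.0:

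> Staff will look at the skin at each electrode site (earlobe for sham) before attachment, at any reported discomfort, numbness or change of ear, and at removal, identically in both groups, and will record none / redness / blister or burn / other skin break. Any blister, burn or skin break is handled as an adverse event under section 13.0.

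The look before attachment separates existing marks from new ones. The separate level for blister or burn is needed because a burn can leave the skin unbroken.

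Costs and limits:

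- Two sentences of protocol text, one line on the session form, and about one minute per participant, by staff who already handle the electrodes.
- More minor redness will be recorded, some of it from electrode contact or pressure and not from heat.
- The trial is single-blinded, so redness may be graded by staff who know the allocation. A difference in redness between groups should be read with that in mind.
- The change improves recording. A burn that is not felt during the 30 minutes would still be found only at removal.
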